8.4 Primary Efficacy Endpoint(s) and Analyses

8.4.1 Primary Efficacy Endpoint(s)

The co-primary endpoints for the primary analysis of efficacy are:

- **For US specific protocol:**
 - The achievement of CDAI clinical remission at Week 12
 - The achievement of endoscopic response at Week 12
- **For global protocol outside US:**
 - The achievement of clinical remission at Week 12
 - The achievement of endoscopic response at Week 12

The primary estimand for US specific protocol is the following:

- Difference in the percentage of subjects achieving CDAI clinical remission at Week 12 regardless of premature discontinuation of study drug and without initiation or dose escalation of CD-related corticosteroids (See Section 8.2.2) in each of the risankizumab 1200mg IV and risankizumab 600mg IV groups in comparison with the placebo group in the ITT1A population
- Difference in the percentage of subjects achieving endoscopic response at Week 12 regardless of premature discontinuation of study drug and without initiation or dose escalation of CD-related corticosteroids (See Section 8.2.2) in each of the risankizumab 1200mg IV and risankizumab 600mg IV groups in comparison with the placebo group in the ITT1A population.

The primary estimand for global protocol outside US is the following:

- Difference in the percentage of subjects achieving clinical remission at Week 12 regardless of premature discontinuation of study drug and without initiation or dose escalation of CD-related corticosteroids (See Section 8.2.2) in each of the risankizumab 1200mg IV and risankizumab 600mg IV groups in comparison with the placebo group in the ITT1A population

- Difference in the percentage of subjects achieving endoscopic response at Week 12 regardless of premature discontinuation of study drug and without initiation or dose escalation of CD-related corticosteroids (See Section 8.2.2) in each of the risankizumab 1200mg IV and risankizumab 600mg IV groups in comparison with the placebo group in the ITT1A population.

Details in estimand definition are outlined in [Appendix J](#).

8.4.2 Handling of Missing Data for the Primary Efficacy Endpoint(s)

The NRI-C approach for handling missing data will be used for primary analysis for the co-primary endpoints for the 12-Week Induction Period.

The NRI-NC and PMM approaches for handling missing data will be conducted as sensitivity analyses for the co-primary endpoints for the 12-Week Induction Period if applicable. For PMM approach, the pre-specified missing-data patterns are given as below. Other missing data patterns could be explored if deemed necessary.

| Missing-data Patterns |
|---|
| Non-completers (missing at Week 4 or at Week 8 or at Week 12) |
| Completers |

8.4.3 Primary Efficacy Analysis

The co-primary endpoints will be analyzed between placebo and each of risankizumab 600 mg IV and 1200 mg IV groups using the CMH test, stratified by the randomization factors of number of prior biologics failed (0, 1, > 1) and baseline steroid use (Yes, No) based on ITT1A. A CMH based two-sided 95% CI for the difference between treatment groups will be constructed.

8.4.4 Additional Analyses of the Primary Efficacy Endpoint(s)

For the co-primary efficacy endpoints, an additional analysis using the same CMH test will be performed using As Observed (AO) data handling without any imputation. The analysis will be conducted using the ITT1A population.

8.5 Secondary Efficacy Analyses

8.5.1 Key Secondary Efficacy Analyses

The estimands corresponding to the secondary efficacy endpoints are defined in Section 2.1. Details in estimand definition for the key secondary endpoints are outlined in [Appendix J](#).

In general, continuous secondary efficacy endpoints with repeat measurements will be analyzed using a MMRM model including factors for treatment group, visit, visit by treatment interaction, stratification variables and the continuous fixed covariates of baseline measurement. The MMRM analysis is considered primary for inferential purposes. Continuous secondary efficacy variables which are collected at only one post-baseline visit (such as SES-CD) will be analyzed using ANCOVA-C approach.

Categorical secondary efficacy variables will be analyzed using the CMH test controlling for stratification variables (prior biologics failed [0, 1, > 1] and baseline steroid use [Yes, No]), except for the endpoints related to draining fistulas and CD-related hospitalization. A CMH based two-sided 95% CI for the difference between each risankizumab treatment group and placebo group will be constructed. The endpoints of "The achievement of no draining fistulas at Week 12 in subjects with draining fistulas at baseline" and "Occurrence of CD-related hospitalization through Week 12" will be analyzed using Chi-square test (or Fisher's exact test if $\geq 20\%$ of the cells have expected cell count < 5).

The NRI-C method will be the primary approach for missing data handling for categorical secondary endpoints except for CD-related hospitalization and draining fistulas. The endpoint of "The achievement of no draining fistulas at Week 12 in subjects with draining fistulas at baseline" will be analyzed using NRI-NC as the primary approach due to the

small sample size. The endpoint of "Occurrence of CD-related hospitalization through Week 12" will be analyzed based on the observed data using AO approach only.

In addition, NRI-NC for missing data handling will be applied as sensitivity analyses for the binary secondary endpoints except for CD-related hospitalization and draining fistulas endpoints.

Analysis of PMM will also be performed as sensitivity analyses for ranked secondary endpoints as appropriate. Analysis of PMM will not be performed for the endpoint of "The achievement of no draining fistulas at Week 12 in subjects with draining fistulas at baseline" due to the small sample size.

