3.0 Endpoints

Below are the definitions of the endpoints used in the efficacy analysis:

- **Clinical remission:** average daily SF ≤ 2.8 and not worse than baseline AND average daily AP score ≤ 1 and not worse than baseline
- **Enhanced clinical response:** $\geq 60\%$ decrease in average daily SF and/or $\geq 35\%$ decrease in average daily AP score and both not worse than baseline, and/or clinical remission
- **Clinical response:** $\geq 30\%$ decrease in average daily SF and/or $\geq 30\%$ decrease in average daily AP score and both not worse than baseline
- **Endoscopic response:** decrease in SES-CD $> 50\%$ from baseline (or for subjects with isolated ileal disease and a baseline SES-CD of 4, at least a 2 point reduction from baseline), as scored by central reviewer

- **Ulcer-free endoscopy:** SES-CD ulcerated surface subscore of 0 in subjects with SES-CD ulcerated surface subscore ≥ 1 at baseline, as scored by a central reviewer
- **Endoscopic remission:** SES-CD ≤ 4 and at least a 2 point reduction versus baseline and no subscore greater than 1 in any individual variable, as scored by a central reviewer
- **CDAI clinical response:** reduction of CDAI ≥ 100 points from baseline
- **CDAI clinical remission:** CDAI < 150
- **SF remission:** average daily SF ≤ 2.8 and not worse than baseline
- **AP remission:** average daily AP score ≤ 1 and not worse than baseline

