3.2 Secondary Endpoint(s)

For US-specific protocol, the secondary endpoints under overall type I error control are:

1. The achievement of clinical remission at Week 12
2. The achievement of CDAI clinical response at Week 4
3. The achievement of CDAI clinical response at Week 12

4. Change from baseline in Functional Assessment of Chronic Illness Therapy-Fatigue (FACIT-Fatigue) at Week 12
5. The achievement of CDAI clinical remission at Week 4
6. The achievement of CDAI clinical response and endoscopic response at Week 12
7. The achievement of SF remission at Week 12
8. The achievement of AP remission at Week 12
9. The achievement of endoscopic remission at Week 12
10. The achievement of enhanced clinical response at Week 4
11. The achievement of ulcer-free endoscopy at Week 12
12. The achievement of enhanced clinical response at Week 12
13. The achievement of resolution of extra-intestinal manifestations (EIMs) at Week 12, in subjects with any EIMs at baseline
14. Occurrence of CD-related hospitalization through Week 12
15. The achievement of no draining fistulas at Week 12 in subjects with draining fistulas at baseline

For global protocol outside US, the secondary endpoints under overall type I error control are:

1. The achievement of CDAI clinical remission at Week 12
2. The achievement of CDAI clinical response at Week 4
3. The achievement of clinical remission at Week 4
4. The achievement of CDAI clinical response at Week 12
5. Change from baseline in FACIT-Fatigue at Week 12

6. Change from baseline in Inflammatory Bowel Disease Questionnaire (IBDQ) total score at Week 12
7. The achievement of enhanced clinical response and endoscopic response at Week 12
8. The achievement of endoscopic remission at Week 12
9. The achievement of enhanced clinical response at Week 4
10. The achievement of ulcer-free endoscopy at Week 12
11. The achievement of enhanced clinical response at Week 12
12. The achievement of resolution of EIMs at Week 12, in subjects with any EIMs at baseline
13. Occurrence of CD-related hospitalization through Week 12
14. The achievement of no draining fistulas at Week 12 in subjects with draining fistulas at baseline
15. Change from baseline in Work Productivity and Impairment Questionnaire – Crohn's disease (WPAI-CD) Overall Work Impairment at Week 12
16. Change from baseline in Short Form-36 (SF-36) Physical Component Summary (PCS) score at Week 12

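### SF remission and AP remission (US ranked endpoints 7 and 8) can count subjects already at target at baseline, and their CMH test does not use that status: valid, but a cheap gain in precision and clarity is missed

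*SAP*

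**What the plan says.** Section 3.2 lists "The achievement of SF remission at Week 12" and "The achievement of AP remission at Week 12" as seventh and eighth of the US secondary endpoints under type I error control. Section 3.0 defines them as "average daily SF ≤ 2.8 and not worse than baseline" and "average daily AP score ≤ 1 and not worse than baseline". Neither is restricted to subjects above the threshold at baseline, and Section 8.1 places the ranked endpoints in ITT1A.

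Section 8.5.1 gives the test: "Categorical secondary efficacy variables will be analyzed using the CMH test controlling for stratification variables". The strata are number of prior biologics failed (three levels) and baseline steroid use (two levels). No baseline SF or AP term appears.

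The plan deals with baseline status elsewhere. Ulcer-free endoscopy is defined as "SES-CD ulcerated surface subscore of 0 in subjects with SES-CD ulcerated surface subscore ≥ 1 at baseline". The EIM and draining-fistula endpoints (Section 3.2) and the minimal-or-absent PGIS endpoint (Section 3.3) are limited in the same way. Sections 8.3.2 and 8.5.1 adjust repeated continuous endpoints for the baseline measurement.

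**The concern.** The requirement not to be worse than baseline can bind only for a subject who starts at or below the threshold. Anyone starting above SF 2.8 or AP 1 who reaches the target has necessarily improved. The definitions therefore provide for subjects at target at entry, who can meet the endpoint without improving. Clinical remission is less exposed, because a subject at target on one symptom must still meet the criterion on the other.

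Two things are at stake:

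- **Precision.** If at-target status predicts the Week 12 result, leaving it out of the CMH strata puts explainable variance into the test and lowers power.
- **Interpretation.** The reported rate mixes new remission with baseline status that was kept, and no planned output separates them. Section 8.7 has baseline SF and AP subgroups, but only for the co-primary endpoints and split at the median.

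**Working it through.** **Inputs from the SAP.** Section 2.4 gives 342 subjects per risankizumab group, 171 on placebo and a two-sided level of 0.025. The level that reaches endpoints 7 and 8 depends on Figure 2, which could not be read in the text reviewed, so 0.025 is an assumption for them. The SAP gives no share at target, no SF or AP remission rate and no power for these endpoints. All such values below are assumptions.

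**The plan's own figure first.** For clinical remission, 27.8% vs 12%, Section 2.4 states 97% power. Exact enumeration of Fisher's test gives 97.7%, the normal approximation 97.9% and the continuity-corrected approximation 97.1%. The stated figure is reproduced.

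**Formula.** For stratum *s* with n_T and n_C subjects, w = n_T·n_C/(n_T+n_C), and p̄ is the pooled rate. Then:

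- numerator D = Σ w(p_T − p_C)
- null variance V0 = Σ w·p̄(1 − p̄)
- alternative variance V1 = Σ w²[p_T(1−p_T)/n_T + p_C(1−p_C)/n_C]
- power = Φ((D − 2.2414·√V0)/√V1)

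The six randomization strata are collapsed, because the SAP gives no rates by stratum for these endpoints.

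**Worked example.** Assume 20% at target, 32% vs 20% remission among those not at target, and 60% vs 50% among those at target.

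- Overall rates: 0.8×0.32 + 0.2×0.60 = 0.376, and 0.8×0.20 + 0.2×0.50 = 0.260.
- Status ignored: w = 342×171/513 = 114. D = 114×0.116 = 13.224, √V0 = 5.048, √V1 = 4.852. Power = Φ((13.224 − 11.315)/4.852) = 65.3%.
- Status as a stratum: w = 91.2 and 22.8. D = 91.2×0.12 + 22.8×0.10 = 13.224, √V0 = 4.897, √V1 = 4.687. Power = Φ((13.224 − 10.977)/4.687) = 68.4%.
- Gain: 3.1 points.

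**Gain in power (points) by share at target:**

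| Not at target | At target | 5% | 10% | 20% | 30% |
|---|---|---|---|---|---|
| 32% vs 20% | 60% vs 50% | 1.0 | 1.8 | 3.1 | 3.9 |
| 37% vs 25% | 62% vs 50% | 0.7 | 1.3 | 2.2 | 2.8 |
| 32% vs 20% | 65% vs 55% | – | 3 | 5 | 5 |
| 37% vs 25% | 82% vs 75% | 2.3 | 4.7 | 7.6 | 9.5 |
| 32% vs 20% | 85% vs 80% | 3.8 | 6.9 | 11.2 | 13.9 |

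The first two rows use the formula. The last three come from simulated trials (20,000 or 40,000 per scenario) comparing six randomization strata with those six plus one at-target stratum. The two methods agree: for the last row at 20%, simulation gives 53.4% to 64.6% and the formula 53.2% to 64.7%. With 32% vs 20% and 82% vs 75%, simulated power rises from 57% to 67% at 20% and from 51% to 64% at 30%.

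**If overall rates are held at 35% vs 25% instead,** the gain is 0.2–2.2 points with 40% placebo response at target. With 60% it is 2.0–3.1 points at 10% at target and 8.9–13.9 points at 30%. The largest values (33–41 points) need 80% response and 30% at target. That leaves (0.25 − 0.30×0.80)/0.70 = 1.4% placebo response among the rest, which is extreme.

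**At the SAP's effect sizes for other endpoints,** the gain is 0.0–2.1 points for 27.8% vs 12% and 0.0–0.4 points for 37% vs 17%. Power there is already 97.9% and 99.6%, so little remains to be gained.

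**Checks on the change itself.** When the status is not prognostic, simulated power is 74.0% without it and 74.1% with it. Under the null, rejection is 0.0249 and 0.0247 against 0.025.

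**The case against.** The strongest reply is that nothing here is wrong. CMH on the randomization factors is valid, and the co-primary endpoints use the same strata. That stands: this is a point about efficiency and reporting.

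A reader might go further in three ways that the SAP does not support.

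- **That at-target subjects are near-automatic responders.** They are not. A subject at SF 1.5 who records 1.6 fails. With true SF uniform from 0 to 2.8 and a noise SD of 0.3–0.5 (assumed), only 48–49% of stable subjects would meet the endpoint. Ties at zero, plausible for AP, would raise this; non-responder imputation and the corticosteroid rule would lower it. This is why about 50% is a reasonable central case and 75–80% is not.
- **That the plan loses some 2–14 points of power.** That range needs the 75–80% response and an effect of 12 points among subjects not at target. The only related effects in Section 2.4 are 15.8 and 20 points, for other endpoints. The at-target share depends on entry criteria that are not in the SAP.
- **That failure on endpoints 7 or 8 blocks those behind them.** Section 11.0 describes ordered testing, but also split arrows, transfer between doses and a final Holm group. Without the figure the role of these two endpoints cannot be verified.

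Interpretation is also partly covered. Section 3.3 plans change from baseline in average daily SF and AP at Weeks 4, 8 and 12, analysed with baseline adjustment. That shows mean improvement but does not split the ranked remission rates.

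**Conclusion.** The point holds as a low-cost improvement. Both endpoints can count subjects at target at entry, and the planned test does not use that status. Type I error is unaffected.

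The power at stake runs from about 0, through roughly 1–4 points in the central case (5–30% at target, about 50% placebo response among them), to above 10 points. With 20–25% placebo response among subjects not at target, exceeding 10 took both 75–80% response at target and 20–30% of subjects at target. At the SAP's effect sizes for other endpoints the gain is at most about 2 points. None of these is a property of the plan; each rests on a share and on rates that the SAP does not give.

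The interpretation point needs no power assumption: the ITT1A rate alone cannot show how much of it is new remission.

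**What to change.** Before unblinding, add to Section 8.5.1 that for SF remission and AP remission at Week 12 the CMH test and the Mantel-Haenszel risk difference are also stratified by baseline at-target status (SF ≤ 2.8, or AP ≤ 1, respectively: yes/no), on top of the two randomization factors.

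Pre-specify when randomization strata are pooled among at-target subjects, and pool only where cells are sparse. The rule is needed: with 5% at target, placebo has 171×0.05 = 8.55 such subjects over six strata, about 1.4 each. Putting all at-target subjects in one stratum regardless of numbers would drop the randomization factors for them without need.

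Report, by treatment group, the remission rate among subjects not at target at baseline beside the ITT1A rate.

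Population, endpoint definitions and estimand stay as they are. The cost is a few sentences of SAP text and one derived flag per endpoint from baseline values that Section 7.1 already summarizes. The small downside is a stratum that is not a randomization factor and some possible pooling.

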8.5.2 Supportive Secondary Efficacy Analyses

For the categorical secondary efficacy endpoints, the same CMH analysis will be repeated using As Observed (AO) data handling without any imputation as an additional analysis. The analysis will be conducted using the ITT1A population.

8.6 Additional Efficacy Analyses

Other continuous and categorical efficacy endpoints for the 12-Week Induction Period will be analyzed using ITT1A similarly as the secondary efficacy endpoints as described in Section 8.5. No multiplicity adjustment will be performed. The chi-square test (or Fisher's exact test if $\geq 20\%$ of the cells have expected cell count < 5 for analyses of binary outcomes) will be used for the following endpoints:

- Patient Global Impression of Severity (PGIS) response at Week 4, Week 8, Week 12 respectively
- Patient Global Impression of Change (PGIC) response at Week 4, Week 8, Week 12 respectively
- The achievement of no draining fistulas at Week 4, Week 8, Week 12 respectively, in subjects with draining fistulas at baseline
- The achievement of no non-draining fistulas at Week 4, Week 8, Week 12 respectively, in subjects with non-draining fistulas at baseline

- The achievement of no anal fissure at Week 4, Week 8, Week 12 respectively, in subjects with anal fissure at baseline

PGIC response and PGIS response endpoints will be analyzed based on the observed data using AO approach. The draining fistulas endpoint, non-draining fistulas endpoint and anal fissure endpoint will be analyzed using NRI-NC approach due to the small sample size.

Analyses for other efficacy endpoints as specified in Section 3.3 for Induction Period 2 will be performed using ITT2A for exploratory purpose. Point estimate and 95% CI for each treatment group as well as point estimate and 95% CI for pairwise treatment differences (i.e., risankizumab 1200mg IV – risankizumab 360mg SC, risankizumab 1200mg IV – risankizumab 180mg SC, risankizumab 360mg SC - risankizumab 180mg SC) will be presented based on the observed data for randomized subjects using AO approach. The subjects in the non-randomized risankizumab 1200mg IV group, who took the placebo in the 12-Week Induction Period, will be displayed separately using descriptive statistics. No p-value will be provided.

In addition, the following selected endpoints will be analyzed using ITT1B for exploratory purpose. Point estimate and 95% CI for each treatment group as well as point estimate and 95% CI for treatment differences between each risankizumab group and the placebo group will be presented based on the observed data using AO approach. No p-value will be provided.

- The achievement of CDAI clinical remission at Week 12
- The achievement of clinical remission at Week 12
- The achievement of endoscopic response at Week 12
- The achievement of SES-CD ≤ 2 or 2 points reduction from the baseline at Week 12 among the subjects with baseline eligible SES-CD of ≥ 3 to 6 for ileocolonic or colonic disease or 3 for isolated ileal disease
- The achievement of any reduction in SES-CD at Week 12

Similarly, the following selected endpoints will be analyzed using ITT2B for exploratory purpose. Point estimate and 95% CI for each treatment group as well as point estimate and 95% CI for pairwise treatment differences will be presented based on the observed data for randomized subjects using AO approach. The subjects in the non-randomized risankizumab 1200mg IV group, who took the placebo in the 12-Week Induction Period, will be displayed separately using descriptive statistics. No p-value will be provided.

- The achievement of CDAI clinical remission at Week 24
- The achievement of clinical remission at Week 24
- The achievement of endoscopic response at Week 24
- The achievement of SES-CD ≤ 2 or 2 points reduction from the baseline at Week 24 among the subjects with baseline eligible SES-CD of ≥ 3 to < 6 for ileocolonic or colonic disease or 3 for isolated ileal disease
- The achievement of any reduction in SES-CD at Week 24

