8.0 Efficacy Analyses

8.1 General Considerations

The primary and secondary efficacy endpoints as specified in Section 3.1 and Section 3.2 will be analyzed based on ITT1A for 12-Week Induction Period. The difference between

treatment groups for the primary and ranked secondary efficacy endpoints will be tested with graphical multiplicity adjustment¹ to ensure a strong control of family-wise type I error rate at significance level $\alpha = 0.05$ (two-sided) (see Section 11.0). Analyses of other efficacy endpoints for 12-Week Induction Period as specified in Section 3.3 will be performed using ITT1A at the nominal significance level $\alpha = 0.05$ (two-sided) without multiplicity adjustment.

Analyses for other efficacy endpoints as specified in Section 3.3 for Induction Period 2 will be performed using ITT2A. Since the Induction Period 2 is for exploratory purpose, no multiplicity adjustment will be performed.

For all efficacy endpoints, the descriptive statistics will be provided by period and by treatment group in which the subjects were randomized to at the beginning of each period. The statistics include number of observations, mean, standard deviation, minimum, median, and maximum for continuous variables, and number and percent for discrete variables.

Unless otherwise specified, any subject who is randomized based on a wrong stratum will be analyzed according to the actual stratum the subject belongs to.

When all subjects complete their Week 12/PD visit, the database will be locked and un-blinded for the 12-Week Induction Period. The planned analysis for the 12-Week Induction Period will be performed. This is the only and final efficacy analysis for the 12-Week Induction Period. When all the subjects who enter the Induction Period 2 finish Week 24/PD visit, the database will be locked for the whole study and all the planned analysis for the Induction Period 2 will be performed.

Analysis of Binary Variables:

For binary variables, frequencies and percentages will be reported for each treatment group. Pairwise comparison of each risankizumab group and placebo will be performed using the Cochran Mantel-Haenszel (CMH) test adjusting for stratification factors. If there is a stratum for a treatment group that has no subject in it, a value of 0.1 will be

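### PGIS and PGIC response, which read as ordered categories, are tested with an unstratified chi-square that ignores their order; the loss matters mainly for PGIC

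*SAP*

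**What the plan says.** The default comes first. Section 8.1 states for binary variables: "Pairwise comparison of each risankizumab group and placebo will be performed using the Cochran Mantel-Haenszel (CMH) test adjusting for stratification factors". Section 8.5.1 repeats it for the secondary endpoints: "Categorical secondary efficacy variables will be analyzed using the CMH test controlling for stratification variables". Section 8.6 extends this to the other 12-week endpoints, which "will be analyzed using ITT1A similarly as the secondary efficacy endpoints as described in Section 8.5".

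Section 8.6 then makes an exception. A chi-square test, with Fisher's exact test as the sparse-cell fallback "for analyses of binary outcomes) will be used for the following endpoints", covers five items. Two of them are "Patient Global Impression of Severity (PGIS) response at Week 4, Week 8, Week 12 respectively" and "Patient Global Impression of Change (PGIC) response at Week 4, Week 8, Week 12 respectively". The other three are the draining fistula, non-draining fistula and anal fissure endpoints. On missing data, "PGIC response and PGIS response endpoints will be analyzed based on the observed data using AO approach", while the fistula and fissure items get NRI-NC because their samples are small.

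Section 3.3 lists PGIS response and PGIC response without defining them. It lists separately a two-category version of each scale (minimal or absent symptoms on PGIS; very much or much improved on PGIC) and the change from baseline in PGIS.

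**The concern.** The SAP justifies a chi-square or Fisher test elsewhere by a small sample or by few responders (Section 8.1). Neither reason is given for PGIS and PGIC response, which Section 3.3 does not restrict to a baseline subset. The departure from the default is therefore unexplained.

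The two responses read as full category distributions. The dichotomised versions are listed separately, so a binary reading would leave overlapping entries. In addition, the Fisher fallback in Section 8.6 is limited to binary outcomes, a qualifier missing from the parallel sentences in Sections 8.1 and 8.5.1, which concern only binary endpoints. The qualifier makes sense if the Section 8.6 list also holds non-binary items.

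Under that reading, a general chi-square with K categories spreads its power over K − 1 degrees of freedom. The expected effect is a shift toward improvement, which a 1-degree-of-freedom ordered test targets directly. At stake is the chance of detecting such a shift, above all on PGIC.

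**Working it through.** **Anchor.** The SAP states no power for PGIS or PGIC, so there is no figure of its own to reproduce on this point. As a check on the design inputs, exact two-sided Fisher power for clinical remission (Section 2.4: 27.8% vs 12%, 342 vs 171, alpha 0.025) comes to 97.7%, against the stated 97%.

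**Analytic cost of ignoring order.** Inputs: two-sided alpha 0.05 (Section 8.1, nominal, for other endpoints); 5 or 7 categories, which are assumptions because the SAP gives no number. For a pure shift captured by one degree of freedom, the non-centrality is λ = (z₀.₉₇₅ + z_power)². Power of the general chi-square is P(χ²(K − 1, λ) > 95th percentile of χ²(K − 1)).

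| Power of 1-df test | λ | 5 categories (4 df) | 7 categories (6 df) |
|---|---|---|---|
| 80% | (1.960 + 0.842)² = 7.85 | 60% | 52% |
| 90% | (1.960 + 1.282)² = 10.5 | 74% | 67% |

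**Simulation at the planned size.** Inputs: 342 vs 171 (Section 2.4), six strata (3 × 2, Section 8.4.3), 3,000 trials per setting. Assumed, not in the SAP: seven PGIC categories, placebo rates 6/14/24/30/13/8/5%, stratum shares, proportional odds ratios, and mild stratum effects for this table.

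| Odds ratio | Chi-square, 6 df | Mean score, no strata | Mean score, stratified CMH | Top-two binary, stratified CMH |
|---|---|---|---|---|
| 1.0 | 5.1% | 4.9% | 5.1% | 5.7% |
| 1.5 | 38.5% | 64.9% | 66.0% | 42.1% |
| 1.75 | 71.1% | 90.4% | 90.8% | 72.4% |
| 2.0 | 89.3% | 98.4% | 98.3% | 89.2% |
| 2.5 | 99.4% | 100% | 100% | 99.2% |

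**Splitting the loss.** At odds ratio 1.5, using the order adds 64.9 − 38.5 = 26.4 points, and adding the strata on top adds 66.0 − 64.9 = 1.1. With strong assumed stratum effects the strata add 66.4 − 63.6 = 2.8 points at odds ratio 1.5 and 90.4 − 88.1 = 2.3 at 1.75. With no or mild effects the change is about 0 to 1 point. For a binary top-two outcome, stratifying moves power by about −1 to +2 points. Almost all the loss comes from ignoring order.

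**What the companion analyses recover.** None of the companion endpoints is on the chi-square list, so each follows Section 8.5.1. PGIS change from baseline goes to MMRM with the stratification factors, which uses the order. The binary cut-offs of both scales go to stratified CMH, which gives a directional test at one cut only. In the table above, the top-two binary test has about the same power as the 6-df chi-square (42.1% vs 38.5% at odds ratio 1.5; 72.4% vs 71.1% at 1.75). It therefore does not replace an ordered test of PGIC.

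**The case against.** The strongest case on the other side is that this is a redundant analysis of non-ranked endpoints. Both scales already have a stratified, directional test at a binary cut-off, and PGIS has its change-from-baseline model. That stands for PGIS. For PGIC it stands only in part, because no planned analysis uses its full order.

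The term is also undefined, and elsewhere in Section 3 response means a binary achievement. If it does here too, there is no order to ignore and the power loss is about 2 points at most. The separate listing and the binary-outcome qualifier favour the ordered reading without settling it.

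The size is assumed. Category numbers and rates are not in the SAP, a pure shift is the case most favourable to an ordered test, and the gap shrinks to 9 points at odds ratio 2.0 and under 1 point at 2.5.

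A reader might infer more than the SAP supports:

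- That the chi-square has no merit. It holds its size and can detect non-monotone differences.
- That dropping the strata is costly. It is not, as shown above.
- That every other large-sample endpoint is stratified. CD-related hospitalization, a ranked endpoint in ITT1A, also gets a chi-square or Fisher test (Section 8.5.1), there because responders are few.
- That direction would be unknown. The chi-square statistic itself is not directional, but Section 8.1 requires descriptive counts and percentages by treatment group.

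**Conclusion.** The point holds as a minor improvement. Section 8.6 moves PGIS and PGIC response from the SAP's stratified default to a chi-square without strata, gives no reason, and leaves both endpoints undefined. On the better-supported ordered reading, the test is valid but insensitive to the expected shift: 80% power on 1 degree of freedom falls to about 60% with 5 categories or 52% with 7. The strata account for only about 0 to 3 points.

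These sizes rest on assumed category numbers, assumed PGIC rates and a pure or proportional-odds shift. The practical consequence falls mainly on PGIC. A reader might infer that the trial's efficacy conclusions are affected. They are not: these endpoints lie outside the type I error control of Section 11.0 and are tested at a nominal 0.05.

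**What to change.** Define PGIS response and PGIC response in Section 3.3, and remove both from the chi-square list in Section 8.6.

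- **If the ordered distributions are meant:** test them with the CMH row-mean-scores statistic, or the van Elteren test, stratified by prior biologics failed (0, 1, >1) and baseline steroid use (Yes, No). State the scores to be used. The as-observed handling can stay.
- **If a binary response is meant:** use the default stratified CMH test, and say how the endpoint differs from the dichotomised versions already listed.

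The cost is a definition and one line in Section 8.6, with the same data. The one small loss is lower sensitivity to non-monotone differences, which the frequency tables by treatment group will still show.
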